H2020	Horizon 2020
ICH	International Conference on Harmonisation
IVDR	In Vitro Diagnostic Medical Devices Regulation
LPFV	Last Patient First Visit
LPLV	Last Patient Last Visit
MCI	Mild Cognitive Impairment
MDCG	Medical Device Coordination Group
MDR	Medical Device Regulation
MEG	Magnetoencephalography
MMSE	Mini Mental State Examination
MoCA	Montreal Cognitive Assessment
NEM	Nasjonale Forskningsetiske Komité for Medisin og Helsefag
NIA-AA	National Institute on Aging - Alzheimer's Association
PET	Positron Emission Tomography
PI	Principal Investigator
REK	Regionale Komiteer for Medisinsk og Helsefaglig Forskningsetikk
SOA	State of Art
SPECT	Single photon-emission computed tomography
SSD	Services for Sensitive Data
TSD	Tjenester for Sensitive Data (in Norwegian: Services for Sensitive Data)
UiO	Universitetet I Oslo (in Norwegian: University of Oslo)
WP	Work Package

Partner Short Names

OUS	Oslo University Hospital
accelCH	accelopment Schweiz AG
AE	Alzheimer Europe
Brainsymph	BrainSymph AS
DNV	Det Norske Veritas
нин	Helsinki University Hospital

IRCCS	Scientific Institute for Research, Hospitalization and Healthcare, San Raffaele Roma
Neuroconnect	Neuroconnect Srl
TLU	Tallin University
UCM	Complutense University of Madrid
UCSC	Università Cattolica del Sacro Cuore

Definitions

Anonymisation	the process by which personal data is irreversibly altered/anonymised in such a way that a data subject can no longer be identified directly or indirectly, either by the data controller alone or in collaboration with any other party.
Biometric data	personal data resulting from specific technical processing relating to the physical, physiological or behavioural characteristics of a natural person, which allow or confirm the unique identification of that natural person (The European Parliament and the Council of the European Union. General Data Protection Regulation - article 4).
Consent	means any freely given, specific, informed and unambiguous indication of the data subject's wishes by which he or she, by a statement or by a clear affirmative action, signifies agreement to the processing of personal data relating to him or her (The European Parliament and the Council of the European Union. General Data Protection Regulation - article 4).
CANTAB	computerised neuropsychological testing (Cambridge Neuropsychological Test Automated Battery).
Genetic data	personal data relating to the inherited or acquired genetic characteristics of a natural person providing unique information about the physiology or the health of that natural person and which result, in particular, from an analysis of a biological sample from the natural person in question (The European Parliament and the Council of the European Union. General Data Protection Regulation - article 4).
Personal Data	any information relating to an identified or identifiable natural person ('data subject'); an identifiable natural person is one who can be identified, directly or indirectly, in particular by reference to an identifier such as a name, an identification number, location data, an online identifier or to one or more factors specific to the physical, physiological, genetic, mental, economic, cultural or social identity of that natural person (The European Parliament and the Council of the European Union. General Data Protection Regulation - article 4).
Processing	any operation or set of operations which is performed on personal data or on sets of personal data, whether or not by automated means, such as collection, recording, organisation, structuring, storage, adaptation or alteration, retrieval, consultation, use, disclosure by transmission, dissemination or otherwise making available, alignment or combination, restriction, erasure or destruction (The European Parliament and the Council of the European Union. General Data Protection Regulation - article 4).
Processor	a natural or legal person, public authority, agency, or other body which processes personal data on behalf of the controller (The European Parliament and the Council of the European Union. General Data Protection Regulation - article 4).
Profiling	any form of automated processing of personal data consisting of the use of personal data to evaluate certain personal aspects relating to a natural person, in particular to analyse or

	predict aspects concerning that natural person's performance at work, economic situation, health, personal preferences, interests, reliability, behaviour, location or movements (The			
	European Parliament and the Council of the European Union. General Data Protection			
	Regulation - article 4).			
Prospective Data	data collected from participants enrolled in the AI-Mind clinical study. Data from 1000 MCI			
	subjects, who will undergo multiple (four times over two years) MEG, EEG and CANTAB			
	testing, and once genetic (APOE4) and P-tau 181 tests, during the project.			
Pseudonymisation	the processing of personal data in such a manner that the personal data can no longer be			
	attributed to a specific data subject without the use of additional information, provided that			
	such additional information is kept separately and is subject to technical and organisational			
	security measures to ensure that the personal data are not attributed to an identified of			
	identifiable natural person (The European Parliament and the Council of the European			
	Union. General Data Protection Regulation - article 4)			
Retrospective	data originating from multiple data controllers, which can be shared beyond the scope of			
Data	the original project they were collected for, based on the subjects' informed consent. In Al-			
	Mind, retrospective data will be shared by four of the five clinical partners (excluding HUS).			
TSD Platform	Centralised secure database provisioned in TSD (located at the University of Oslo, Norway),			
	where AI-Mind data will be collated and processed.			

1 Executive Summary

The aim of WP5 is to collect standardised, prospective data in order to validate and refine the final Al-Mind Connector and Al-Mind Predictor tools. The data will be collected through a clinical study that will recruit people with Mild Cognitive Impairment (MCI). The study will be implemented in five clinical sites in Finland (HUS), Italy (IRCCS/UCSC), Norway (OUS), and Spain (UCM).

1.1 Purpose and Scope of the Deliverable

Deliverable 5.1 is part of task 5.1: "Preparation and implementation of the observational study". Al-Mind's clinical study will recruit people with symptoms of MCI to collect medical data that will be used for the development of the AI algorithms and the validation of the AI-Mind Connector and Predictor tools.

This deliverable provides information about the clinical study dossier, more specifically about the background and standardised clinical procedures, according to which the clinical study will be implemented. The outcomes of the deliverable are based on a process of employed methodologies used to make the enrolment, procedures, and administration of all tests homogeneous among the participating clinical sites.

1.2 Outcomes

The main outcomes regarding the Clinical Study Dossier and clinical study procedures are summarised below.

Inclusion and exclusion criteria

The definition of inclusion and exclusion criteria is based on an extensive literature review and the internal Al-Mind partners` agreement to adhere to the project's objectives.

Definition of MCI at enrolment

General consensus of the criteria to define MCI for the clinical study participants. The inclusion criteria define the degree of cognitive impairment and a minimum of test assessments (table 2).

Ethical requirements and Informed Consent before enrolment

All clinical sites followed the local ethical procedures in alignment with relevant national and EU laws and regulations. An independent Al-Mind ethics advisor has been appointed. Feedback from the user representing association Alzheimer Europe has been implemented.

Ethical Committee approvals

The study has been approved by the Ethical Committees of all clinical sites in due course. The final consensus of the used clinical guidelines, procedures and formation have been incorporated into the application. All Informed Consents have been approved.

Definition of demographic and clinical data collection

Various clinical variables (e.g. demographics, weight, etc.), information about well documented associated pathologies and interventions will be collected. These data will be analysed in order to determine their influence on the risk of progression to dementia for population with MCI.

Blood sample collection, storage and shipment

Blood samples will be collected at the first visit, to determine their APOE allele constellation and individual P-Tau associated P181 and/or P217 protein levels. The samples will be collected, stored and shipped according to standardised procedures (Deliverable 2.1).

Harmonisation of EEG recording and storage

All technological aspects for the EEG recording have been standardised and agreed on among the experts from the five clinical sites. All sites will use identical 128-channel EEG devices and harmonised recording parameters (amplification, sampling rate, filters, artefact recognition, duration of each session etc). The characteristics of the recording environment (baseline noise/light brightness) have been standardised (Deliverable 2.1).

Digitalised Cognitive Testing (CANTAB)

All clinical sites will use standardised digital cognitive tests (CANTAB). The tests will be digitally administered in all national languages by electronic tablets (iPads), provided to the participants during the study visits.

2 Introduction

Al-Mind is a five-year EU funded (Horizon2020) project aiming to deliver innovative solutions that will support the definition and diagnosis of the risk to progress to dementia for people who are at the onset of cognitive impairment. The objective is to create an Al-supported cloud-based diagnostic platform that integrates non-invasive, widely available and low-cost state-of-the-art (SOA) technologies. The two integrated Al-Mind tools - Connector and Predictor - will improve and advance the early risk detection to progress to dementia for people affected by Mild Cognitive Impairment (MCI).

In Al-Mind Connector the main objective is to detect synaptic dysfunctions by empowered EEG-based analysis of functional network maps, using Al algorithms. The Al-Mind Connector outcome will be further enriched with other markers of progression to dementia, i.e. blood biomarkers, genetic risk assessment, and computerised cognitive testing, resulting in a second tool, the Al-Mind Predictor, that will finally estimate the risk for progression to dementia for people with MCI.

2.1 WP5 and Deliverable 5.1

The objective of WP5 is to implement and validate Al-Mind Connector and Predictor. This will be achieved through a clinical study that will take place in five European clinical sites: HUS (Finland), IRCCS and UCSC (Italy), OUS (Norway), and UCM (Spain). The collected prospective data (in addition to the classical SOA clinical procedures), will be transferred and analysed on the SSD (Services for Sensitive Data) server at the University of Oslo (UiO – the server is specifically called TSD, according to the translation of SSD in Norwegian).

In the Deliverable 5.1 (Clinical Study Dossier) the following elements and procedures are defined:

- Clinical study overview
- Definition of inclusion and exclusion criteria
- Inclusion process and data collection (including textual data)
- EEG recordings
- Blood sample collection, storage and shipment
- Digital Cognitive testing (CANTAB)
- Harmonisation procedures, deployed to achieve a uniform study implementation to all clinical sites
- Ethical principles and procedures in clinical sites.

3 Clinical Study

3.1 Summary

The aim of this observational, naturalistic study is to validate AI-based tools used for an innovative approach to early dementia risk estimation.

Today, we know that about 50% of patients with MCI are at risk of developing dementia. Early risk signs include functional brain network disturbances as an expression of synaptic dysfunction/failure in the earliest course of potential dementia development. This synaptic dysfunction can be explored by electrophysiological brain signals. The Al-Mind Connector algorithm will identify such functional brain networks in an automated manner using the Graph theory, among other mathematical possibilities. Classical machine and deep learning approaches of artificial intelligence will be deployed by automating these brain network identifications. The Al-Mind Predictor will serve as an enriched Connector, by applying prospectively data from a sample of 1000 MCI participants in a multimodal prediction method for risk estimation. Enrichment is achieved by including digital cognitive tests, APOE alleles genotyping and plasmatic P-Tau protein level information to develop the Al-Mind Predictor algorithm. The Al-Mind Predictor will discriminate between MCI-prodromal-to-dementia patients and MCI-non-prodromal-to-dementia subjects. The results of the anticipated, highly sensitive Al-Mind Predictor will be compared to state-of-the-art (SOA) approaches.

The new technology will not compete with existing diagnostic tools for dementia (CSF, fMRI, PET, SPECT), because AI-Mind wishes to take its role as an early predictive screening method, increasing the percentage of correctly selected MCI subjects for further invasive or more costly diagnostics, resulting in earlier intervention. Importantly, AI-Mind's new data handling procedures only use existing, well-established, globally accessible and low-cost SOA technologies. With AI-Mind's new data processing approach, the goal is to increase today's low predictive value (<0.5) of the SOA-based clinical dementia prediction, and proactively select with higher accuracy than before, MCI-prodromal patients for further clinical intervention. Thereby, AI-Mind wishes to contribute to delaying dementia development by detecting the risk at the first visit when symptoms occur.

The cutting-edge of the Al-Mind model development and testing will be done by available retrospective and new prospective data collected at the five clinical centres. The 1000 MCI subjects will be recruited as follows: 250 participants at HUH, OUS, and UCM, and 125 at IRCCS and UCSC. All participants will provide signed Informed Consent before entering the study and will be tested 4 times.

The participants will follow a 2-year Al-Mind protocol in parallel with their usual SOA follow-up visits at each hospital (table 3, Schedule of Activities). The protocol includes 4 repetitive electrophysiological measurements (EEG), 4 digitalised cognitive testing (CANTAB); and at the first visit, blood sample collection for APOE allele genotyping and p-Tau analyses. At two of the clinical sites (HUH and UCM), in a subgroup of participants, additional magnetoencephalography measures (MEG) will be analysed for specific feature extraction for modelling the EEG based Al-Mind Connector technology (see table 1).

3.2 Primary and Secondary Objectives of the Clinical Study

The objectives and endpoints of the observational study in the AI-Mind project are listed in table 1.

Table 1: Main objectives and endpoints of the AI-Mind Clinical Study

Objectives	Endpoints		
Primary			
 To validate the Al-Mind Connector as a tool for early brain network connectivity disturbance in at-high-risk MCI subjects. To validate the Al-Mind Predictor as a diagnostic support tool for dementia risk evaluation. 	 Al-Mind Connector with estimated specificity and sensitivity value > 0.9. Al-Mind Predictor with higher prediction value at 24-month for early dementia risk than current clinical practice. Al-Mind Predictor with estimated specificity and sensitivity value > 0.9. 		
Secondary			
 To validate the Al-Mind technology on its economic and social impact on the healthcare sector. To validate the trustworthiness of the Al-Mind technology towards stakeholders. To validate the clinical use of CANTAB together with classical NTP. To validate the accuracy of different M/EEG (connectivity) data features for predicting the risk of dementia. 	 Delivery of a health technology assessment report showing increased impact on economic and social aspects of the AI-Mind technology. Report on the increased clinical value of CANTAB as an assessment tool for clinical evaluation of cognitive function. Report on the predictive value of different M/EEG connectivity measures and of their combinations in dementia risk assessment. 		

Potential important results confounding background/demographic parameters will be documented in the clinical study protocol by each clinical centre and investigated by the AI-Mind tool development team (e.g., age, sex, education, medication, lifestyle, medical history).

3.3 Study population

Approximately 1500 MCI subjects will be screened in order to consecutively enrol 1000 participants according to the clinical criteria and assessments presented in table 2. All subjects will be enrolled according to the local mild cognitive symptom and clinical SOA procedures.

_

¹ the term "enrolled" refers to a participant's, agreement to participate in a clinical study following completion of the Informed Consent process and screening. Potential participants who are screened for the purpose of determining eligibility for the study, but do not participate in the study, are not considered enrolled, unless otherwise specified by the protocol.

Screening procedure

The screening procedure for inclusion in the Al-Mind study consists of two steps:

- Pre- (self-) screening: people who express their interest in participating in the AI-Mind study, will be given a screening questionnaire (in local language) targeting memory impairment. This test may be either self-administered (i.e. accessed electronically through an internet link), or administered by a clinician. In both cases the data will be collected through electronic forms (Nettskjema, see chapter 3.6). Only people who report mild symptoms, will be invited for further screening.
- Professional screening: Following, the potential participants will be given a local inclusion ID
 number and will proceed to the control of inclusion and exclusion criteria, as described
 below. If the subjects qualify for the study, they will be given the AI-Mind participant ID
 number.

Subjects fulfilling the Al-Mind criteria for MCI - based on the acknowledged criteria by the National Institute on Aging-Alzheimer's Association (NIA-AA) - and meeting the Al-Mind inclusion/exclusion criteria (listed below) will be offered participation in the Al-Mind clinical study. In principle, the clinical identification of MCI is defined by the participant's cognitive status. The assessment tools include Mini Mental Status Examination (MMSE), Montreal Cognitive Assessment (MoCA), Clinical Dementia Rating (CDR), Instrumental activities of daily living (IADL), and the Petersen/Winblad criteria (Petersen et al., 2004) (table 2).

Table 2: The criteria used for cognitive evaluation and later potential dementia progression

MCI Criteria	MCI Assessment	Dementia Progression Assessment	
 Cognitive concern reported Objective evidence of impaired cognitive domain Persevered independence in functional abilities (ADCS-ADL >70%) Not demented (cognitive changes do not significantly impede social function or work activities) (Rule out vascular, other causes) Longitudinal decline (no lasting more than 3 years period at the enrolment time) Diagnostic and Statistical Manual of Mental Disorders, Fifth Edition, DSM – 5 	 CDR = 0.5 MMSE ≥ 25 Petersen/Winblad criteria, 1.5 SD in 1 or more domain Additional questionnaires: IADL/ADCS-ADL Montreal cognitive assessment (MoCa, ≥17) 	 CDR >0,5 MMSE ≤ 24 MoCa < 17 Petersen/Winblad criteria, 2 SD in 1 or more domain IADL below the limit of 70% 	

• Clinical Dementia Rating: The CDR® Dementia Staging Instrument uses a 5-point scale to characterise six domains of cognitive and functional performance applicable to dementia. The six domains are Memory, Orientation, Judgment & Problem Solving, Community Affairs, Home & Hobbies, and Personal Care. The rating is done by a semi-structured interview of the tested subject and a reliable informant or collateral source (e.g. a family member) referred to as the CDR® Assessment Protocol. Using the CDR® Scoring Table a subject's level of impairment/dementia is characterized: 0 = Normal, 0.5 = Very Mild Dementia, 1 = Mild Dementia, 2 = Moderate Dementia, 3 = Severe Dementia.

- Deliverable No. **D5.1** Version 1
- Mini Mental State Examination (MMSE): The MMSE is a brief, quantitative measure of cognitive status. It can be used to screen cognitive impairment, to estimate the severity of cognitive impairment at a given point in time, to follow the course of cognitive changes in an individual over time, and to document an individual response to treatment. Measurements of cognitive function include registration (repeating named prompts), attention and calculation, recall, language, ability to follow simple commands and orientation. Score of 24 or more (out of 30) is considered a normal cognition. Below this, scores can indicate severe (≤9 points), moderate (10−18 points) or mild (19−23 points) cognitive impairment.
- Montreal Cognitive Assessment (MoCa): Due to ceiling effects in light MCI cases by the MMSE, the MoCa test will be used as well in assessing people affected by MCI. MoCa is a 30-question test that takes around 10 to 12 minutes to complete. MoCA evaluates cognitive abilities including Orientation, Short term memory/Delayed Recall, Executive Function/Visuospatial Ability, Language Abilities, Abstraction, Animal Naming, Attention and Clock-Drawing Test. Because it tests the executive function, it is considered more sensitive in this regard compared to MMSE.

In addition, the following inclusion and exclusion criteria must be fulfilled to enrol subjects in the study:

Inclusion criteria

- Male and female aged between 60 and 75 years.
- Al-Mind MCI assessment listed in table 2.
- Capable of giving signed Informed Consent, which includes compliance with the requirements and restrictions listed in the Informed Consent and in this protocol.

Exclusion criteria

- AI-Mind dementia criteria listed in table 2.
- History of cerebrovascular disease (i.e., major stroke episodes).
- Alcohol Dependence Scale AUDIT score positive.
- Severe medical disorders associated with cognitive impairment (organ insufficiencies, chronic infections, endocrine disorders) which produce chronic uncompensated failure.
- Severe head trauma with structural brain lesion and/or previous brain surgery.
- Severe mental disorders; Schizophrenia, known Major depression or bipolar disorder.
- Neuroimaging evidence of other potential causes of cognitive decline (e.g. subdural hematoma, brain malignancy, metabolic encephalopathy).
- History of non-brain malignancy < 5 years.
- Recent use of psychotropic drugs including AChEI and Memantine < 3 months.
- Participation in trials with experimental drugs.

The age specification is set between the age of 60 - 75 years at enrolment to avoid increasing confounding factors by age, causing cognitive function loss.

There is a documented dementia uneven prevalence of 2:1 in MCI, affecting females more often than males (The Economist Intelligence Unit Limited, 2017). This epidemiological aspect will be addressed during the AI-Mind AI-tool developments and validation to ensure that relevant gender-associated biomarkers are not omitted. Due to this gender discrepancy, it can be hypothesised that there will be an increased prevalence of female-derived available and prospective data for inclusion, which could result in bias during tool development. Using state of art techniques to mitigate the bias of the AI algorithms development will ensure that the collected data is representative for both genders even though the data might be unbalanced due to the prevalence in female subjects.

Furthermore, unanimously at the General Assembly meeting on the 17th of September 2021, all sites decided to integrate supplemental SOA neuropsychological assessments to pre-screen potential

participants. These evaluations will be administered at each site during recruitment screening, covering different cognitive areas: memory, attention, executive functions, visuospatial skills and language. The scores obtained in these additional neuropsychological assessments will be included in Case Report Forms (CRF, table 3 and Annex I).

Table 3: Schedule of Activities

Procedure	Recruitment screening		Follow-up (weeks/months)			Notes
		то	T1	T2	Т3	
		0	8	16	24	
Informed consent signed	Х					
Inclusion and exclusion criteria	Х					
Sociodemographic and Anamnestic Data	Х					
Clinical history	Х					
Somatic and neurological physical examination	Х	Х	Х	Х	Х	
FFQ (Food frequency questionnaire)		Х				
Risk Factors	Х	Х				
Assessment of Somatic Comorbidity	Х	Х				
Current Therapy	Х	Х	Х	Х	Χ	
Memory Questionnaire	Х	Х			Χ	
AI-Mind MCI criteria, table 3	Х					
RAVLT (Rey Auditory Verbal Learning test)		X			Х	
ROCF (Rey-Osterrieth complex figure test)		Х			х	
Boston Naming Test		Х			Х	
Category Fluency		Х			Х	
TMT (A,B,B-A)		Х			Х	
Letter fluency		Х			Х	
128 lead EEG		Х	Х	Х	Х	
CANTAB – digitalised cognitive assessment		Х	Х	Х	Х	
MEG		Х			Х	only at UCM and HUH
Blood sample collection		Х				APOE, P-tau variance

Subgroup for MEG procedure

At UCM and HUH, a minimum of 70 patients per site will be measured with simultaneous M/EEG recordings. The localisation accuracy of MEG will be used for extracting the most relevant features for EEG data analysis.

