Annex I

CRF – Nettskjema

Al-Mind: Case Report Form for Inclusion

Page 1 Mandatory fields are marked with a star * Clinician's name and contact information The name of the project associate filling in the CRF form (first name and surname)? * Not the participant's name. What is your e-mail address? * Not the participant's email. Page break Page 2 Mandatory fields are marked with a star * **Local Inclusion ID** The *Inclusion ID* is a code used for local management of potential participants *prior* to inclusion into the Al-Mind study. Once the participant is included in the study, they will receive their Participant ID. Don't know the participant's Inclusion ID? Please contact the clinical site Pl. Page break Page 3 Mandatory fields are marked with a star *

INCLUSION CRITERIA CHECKLIST

Age be	etween 60 and 75 years (at the time of inclusion)?
0	Yes
0	No
Cognit	ive concern reported by participant and/or a proxy caregiver? *
0	Yes
0	No
Object abilitie	ive evidence of impaired cognitive domain (yet preserved independence in functional s)? *
0	Yes
0	No
Not de	emented; cognitive changes do not significantly impede social function or work activi-
0	Yes
0	No
Longit	udinal decline (not lasting more than 3 years period at the enrollment time) *
0	Yes
0	No
DSM-	5 diagnosis "MCI" at the time of inclusion? *
0	Yes
0	No

Are vascular (stroke) or other causes of the cognitive impairment ruled out? *

	ŕ
O Yes	
O No	
MMSE ≥ 25 or MoCA ≥ 17? *	
O Yes	
O No	
(I)ADL/ADCS-ADL > 70%? *	
O Yes	
O No	
Petersen/Winblad criteria, 1.5 SD in 1 or more domain fulfilled	d? *
O Yes	
O No	
CDR ≤ 0.5? *	
O Yes	
O No	
Page break	
	Page 4

Mandatory fields are marked with a star *

EXCLUSION CRITERIA CHECKLIST

0	
	Yes
0	No
Alcoho	ol Dependence Scale (e.g. AUDIT) score positive? *
0	Yes
0	No
_	evere medical disorders associated with cognitive impairment (organ insufficiencies, c infections, endocrinical disorders) which produce chronic uncompensated insuffi- ? *
0	Yes
0	No
Any se	evere head trauma with structural brain lesion and/or previous brain surgery? * Yes
0	No
-	evere mental disorders (e.g. schizophrenia, known major depression or bipolar disor-
-	evere mental disorders (e.g. schizophrenia, known major depression or bipolar disor-
-	evere mental disorders (e.g. schizophrenia, known major depression or bipolar disor-
der)?	evere mental disorders (e.g. schizophrenia, known major depression or bipolar disor-

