der)?	evere mental disorders (e.g. schizophrenia, known major depression or bipolar disor- Yes No euroimaging evidence of other potential causes of the cognitive decline (e.g. subdural

History of malignancy < 5 years? *	
O Yes	
O No	
Recent use of psychotropic drugs including AChEI and Memantine (< 3 months)? *	
O Yes	
O No	
MMSE ≤ 24 or MoCa < 17? *	
O Yes	
O No	
Petersen/Winblad criteria, 2 SD in 2/3 cognitive domain/according to MCI criteria *	
O Yes	
O No	
Positiv (I)ADL score (retained function) less than 70%? *	
O Yes	
O No	
Page break	
	Page 5

Mandatory fields are marked with a star *

ASSESSMENT SCALE RESULTS

Cognitive functioning

Cognitive fu	nctioning scale *
Specify which	n scale has been used to assess cognitive functioning .
O MMSE	
O MoCA	
Other (s	specify below)
Specify which	ch assessment scale was used to assess cognitive functioning *
	ment is only shown when the option "Other (specify below)" is selected in stion "Cognitive functioning scale"
Cognitive fu	nctioning scale score *
Ü	the score obtained with the assessment scale.
Activities	of Daily Living (ADL)
ADL scale *	
Specify which	h of the ADL scales has been used.
O IADL	
O ADL-MO	
Other (s	specify below)
Specify which	ch of ADL scales was used *
	ment is only shown when the option "Other (specify below)" is selected in stion "ADL scale"
ADL scale s	score *
Please enter	the obtained positive ADL score (i.e., the percentage of intact function).

Clinical Dementia Rating (CDR)

Use the calculator found here to compute the Global Score.

CDR scale G	Blobal Score *
Please enter t	he obtained CDR-Global Score.
Depressio	n
Depression s	cale *
Specify which	scale has been used to assess depression .
O MADRS	
O GDS	
Other (sp	pecify below)
Specify whicl	h assessment scale was used to assess depression *
This elem	nent is only shown when the option "Other (specify below)" is selected in ion "Depression scale"
Depression s	he score obtained with the assessment scale.
riodoo ontor a	To doore obtained with the doodselfield doubt.
Alcohol ak	ouse
Link to online	AUDIT screening.
Alcohol abus	e scale *
Specify which	scale has been used to assess alcohol abuse .
O AUDIT	
Other (sp	pecify below)
Specify whicl	h assessment scale was used to assess alcohol abuse *
	nent is only shown when the option "Other (specify below)" is selected in ion "Alcohol abuse scale"

Alcohol abuse scale score *	
Please enter the score obtained with the assessment scale.	
E Page break	
	Page

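### Protocol Table 2 and the inclusion CRF set different 2 SD rules, so a participant accepted on the CRF can already meet a dementia-progression item at T0, and the rule for combining the progression items is not stated

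*Protocol*

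**What the plan says.** Three places in the protocol use the neuropsychological cut-off.

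- **Entry.** Section 3.3, Table 2 (MCI Assessment) asks for "Petersen/Winblad criteria, 1.5 SD in 1 or more domain", with no lower bound. The CRF inclusion checklist repeats this: "Petersen/Winblad criteria, 1.5 SD in 1 or more domain fulfilled".
- **Progression and exclusion.** Table 2 (Dementia Progression Assessment) lists "2 SD in 1 or more domain" beside CDR, MMSE, MoCA and IADL items. The exclusion criteria in section 3.3 then name the "AI-Mind dementia criteria listed in table 2".
- **CRF exclusion.** The Annex I checklist has "Petersen/Winblad criteria, 2 SD in 2/3 cognitive domain/according to MCI criteria" as a separate yes/no item.

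Section 3.3 names five domains for the neuropsychological assessment: "memory, attention, executive functions, visuospatial skills and language". Table 1 sets the primary endpoints as 24-month prediction better than current practice and sensitivity and specificity above 0.9. Section 5 assumes about 50% prevalence of each class.

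**The concern.** The Table 2 exclusion and the CRF item disagree about the same person. Someone with one domain at 2 SD is excluded under a single-item reading of section 3.3 but accepted by the CRF exclusion item, and then starts the study already meeting a progression item.

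The progression column also has no rule for combining its five items and no requirement for change from baseline or confirmation. It is the only definition of progression in the document, so it is the natural reference label for the Predictor. If one item is enough, a fall of up to half an SD in any one of five domains turns a stable participant into a case. Such false cases lower the apparent sensitivity of any predictor, however good. The same list also governs drop-out, because section 5 has participants who develop exclusion criteria leave the study.

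**Working it through.** **1. The plan's own figure.** Section 5 states that 1000 participants and 4000 measurements suffice. This cannot be reproduced, because no numerical alpha, interval width or data split is given. For scale, with 500 per class and true sensitivity 0.9 the 95% half-width is 1.96 × √(0.9 × 0.1 / 500) = 0.026. The point here does not depend on N.

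**2. The rules side by side** (a person meeting entry, with k domains at or below -2 SD):

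- k = 0: passes both the Table 2 exclusion item and the CRF item.
- k = 1: meets the Table 2 item, passes the CRF item.
- k = 2: meets the Table 2 item; the CRF result depends on whether 2/3 is read as two domains or three.
- k ≥ 3: meets both.

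The conflict at k = 1 follows from the text alone.

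**3. How often, under assumptions.** The documents give no reliability, inter-domain correlation or mean impairment. Assumed: five domains, observed scores with SD 1, reliability 0.7-0.9, true-score correlation 0-0.5, mean 0 to -1 SD, two occasions with the same true score, and no practice effect. Two occasions match Table 3, which schedules the classical tests at T0 and T3. Simulation with 400,000 people per scenario gives:

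- Protocol-eligible on an any-one reading (at least one domain at or below -1.5 SD, none at or below -2 SD): 0% meet the item at T0 by construction, and 18-45% meet it at the second occasion with no true change.
- CRF-eligible with 2/3 read as two domains (fewer than two at -2 SD): 34-60% already meet the Table 2 item at T0.
- CRF-eligible with 2/3 read as three domains: 37-68%.

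The low ends come from mean 0 and the high ends from mean -1 SD.

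**4. Effect on sensitivity if one item suffices.** Let p be the true progression fraction and f the fraction of stable participants labelled as progressed, with all true progressors labelled correctly. A perfect predictor has apparent sensitivity p / (p + (1 - p)f). With p = 0.5 this is 1 / (1 + f).

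- Sensitivity above 0.9 needs f < 1/0.9 - 1 = 0.111.
- f = 0.18 gives 1/1.18 = 0.85.
- f = 0.45 gives 1/1.45 = 0.69.

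A predictor with true sensitivity and specificity of 0.9 shows (0.9 + 0.1f) / (1 + f): 0.918/1.18 = 0.78 at f = 0.18, and 0.945/1.45 = 0.65 at f = 0.45.

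**5. Is one item enough?** The text does not say. Two features lean that way: the CRF gives the exclusion items separate yes/no answers, and Table 3 lists no MMSE, MoCA, CDR or IADL row at T3 while it repeats the classical tests there. Neither settles the rule for the 24-month outcome, and usual-care visits might supply the other scales.

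**The case against.** A reader might infer that the overlap of the 1.5 SD and 2 SD rules is enough to put progressed people into the cohort. It is not. In the simulation 37-69% of everyone meeting the entry rule also meets the 2 SD item, but on an any-one reading section 3.3 excludes those people. The baseline route runs through the CRF wording only.

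A reader might also infer that one domain at 2 SD with preserved function is labelled dementia, so the 0.9 target is out of reach. The documents do not support that as a certainty. The progression column also lists CDR and IADL, and exclusion on any one item would not show that the outcome uses any one item. If the items are joint or feed a clinical judgement, the retest argument fails. Detail of the binary outcome may also sit in the statistical analysis plan, which is not at hand.

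Nor does the protocol show that sites would label outcomes differently. Annex I is an inclusion form and carries no 24-month label.

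Finally, the percentages rest on assumed inputs, and practice effects would reduce downward crossings. All of this stands. It leaves untouched the conflict between Table 2 and the CRF, and the missing combination rule within Table 2. An analysis plan cannot undo enrolment under a form that contradicts the protocol's exclusion criterion.

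**Conclusion.** The concern holds in a limited form. The contradiction between Table 2, the exclusion criterion and the CRF item is firm and needs no assumption: a participant with exactly one domain at 2 SD passes the CRF item and already meets a progression item at T0. That Table 2 leaves the combination rule and the role of baseline open is also firm.

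The threat to the 0.9 endpoint is conditional on one item being sufficient. On that reading the assumed ranges give chance crossing of roughly 18-45% in stable protocol-eligible participants, against a tolerance of about 11% at 50% prevalence. The tolerance is exceeded throughout the assumed range, but the size within it is uncertain. If several items must be met together, this part falls away.

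**What to change.** - Reconcile Table 2, the exclusion criterion in section 3.3 and the CRF exclusion item so that one rule, in one wording, applies in all three. State what 2/3 means if it is kept.
- State how the five progression items combine for the 24-month outcome, and whether decline from baseline or confirmation is required.
- Count as progression only a status not already met at T0.
- Derive each participant's T0 status from the neuropsychological scores the CRF collects. Report those who meet the item at T0, or exclude them from the outcome analysis.

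The investigators must choose the cut-off and the combination rule; none is proposed here.

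The cost is a wording change to the protocol and CRF, plus a derivation from scores the CRF already provides for. The CRF records raw scores, so the norms used to convert them to SD units must be named. If the chosen rule uses scales that Table 3 does not schedule at T3, the schedule needs changing too. Expect fewer outcome events, and possibly fewer eligible participants if the stricter exclusion is kept.
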